Official Title: Evaluation of Motor Unit Abnormalities after Experimentally Induced Sensitization Using Capsaicin: A Randomized, Double-Blinded, Placebo-Controlled Study

NCT Number: Not Assigned

Date of Document: October 1st, 2019

Abstract

Central sensitization is a condition that represents a cascade of neurological adaptations, resulting in an amplification of nociceptive responses from noxious and non-noxious stimuli. However, whether this abnormality translates into motor output and more specifically, ventral horn abnormalities, needs to be further explored. Twenty healthy participants aged 20-70 will be randomly allocated to topical capsaicin or a placebo topical cream which will be applied onto their left upper back to induce a transient state of sensitization. Visual analogue scale (VAS) ratings of pain intensity and brush allodynia score (BAS) will be used to determine the presence of pain and secondary allodynia. Surface electromyography (sEMG) and intramuscular electromyography(iEMG) will be used to record motor unit activity from the upper trapezius and infraspinatus muscles before and twenty minutes after application of capsaicin/placebo. Motor unit recruitment and variability will be analyzed in the sEMG and iEMG, respectively. An independent t-test will be performed on the data. This preclinical evidence may provide some explanation for the influence of central sensitization on changes in movement patterns that occur in patients who have pain encouraging of further clinical investigation.

Keywords: Central Sensitization; Surface Electromyography; Intramuscular Electromyography; Motor Unit; Recruitment

1. Introduction

Chronic pain is characterized by pain lasting longer than three months [1-3]. It is a common condition affecting 1 in 5 people [4] and is rising due to the aging population and increased prevalence of comorbid conditions such as diabetes [5,6] and obesity [7]. Chronic pain produces

a significant socioeconomical burden with the annual estimated cost in Canada exceeding 6 billion dollars [4,8-11]. As such, the assessment and diagnostic efficacy of chronic pain is of vital importance to improving its management throughout society.

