Central sensitization describes a state of neuronal hyper-excitability in the central nervous system that may occur due to malfunction of spinal and supraspinal pain facilitatory and inhibitory circuits resulting in amplification of somatosensorial responses [12]. Beyond somatosensorial changes, alteration in motor function can also be present with pain, and may be a reflex of neuromuscular function impairment [13,14]. A normal afferent input and normal central processing circuitry is essential to deliver normal efferent output. However, the influence of the changes that occur within the dorsal horn on the ventral horn remain largely ill defined [15,13].

Motor unit assessment is crucial in evaluating diseases and abnormalities within the ventral horn [16]. Activity of the ventral horn, where anterior horn cells reside, is very important for motor unit activation [16]. Surface EMG (sEMG) [17] and intramuscular EMG (iEMG) [18] can be used to assess the neural drive to muscles, by recording motor units to understand the effects of central sensitization on motor control and the ventral horn. Based on Henneman's size principle, motor units should be recruited in the same order, with smaller units being recruited first [19]. This principle presents an opportunity to investigate if central sensitization creates abnormalities on the motor unit level.

Previously, central sensitization has been induced in healthy subjects to examine its neurophysiological effects via capsaicin [20-22]. Capsaicin, a chilli pepper extract, can be used to effectively induce experimental transient states of central sensitization. [23-25,21,22]. The presence of expanded sensorial responses and the involvement of the spinal nociceptive system

post capsaicin have been largely tested by means of quantitative sensory testing methods and electromyography (EMG) [25,21,22,24].

Despite the usefulness of experimental capsaicin to better understand the sensorial abnormalities, its impact on motor function and motor unit recruitment are lesser studied. Evidence suggests that nociceptive input by peripheral capsaicin exerts a centrally-mediated inhibitory effect on motor function [26]. A decrease in root mean squared (RMS) amplitude during exercise at the time of peak sensitization was measured by needle EMG [26]. However, the effect that capsaicin-induced sensitization has on individual motor units or on their recruitment patterns has not been previously examined.

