The motor unit average amplitudes obtained from the *Neuromap* software will be used for calculating an amplitude ratio between pre- and post-recording motor units. This amplitude ratio will be calculated for each pre/post motor unit pair to determine similarities in the amplitude. Similar to the shape analysis, amplitude ratios that are below a preset threshold of 0.8 or above 1.2 are set to 0. This ratio will be normalized to be within a scale from 0 – 1 to allow for comparison between shape and amplitude using the following equation (Eq.1) when the amplitude ratio is above one.

$$\text{Normalized Amp. Ratio} = 1 - \text{Amp. Ratio} \quad (1)$$

The numbers from the shape analysis and amplitude analysis, which are not set to 0, will be averaged together to express an “overall match” between pre- and post- motor units from each participant. As mentioned, based on Henneman’s size principle, motor units should be recruited in the same order with smaller units being recruited first and subsequent motor units are recruited as more force is needed [19]. To observe whether this principle is upheld or violated, the reorganization of the recruitment will be identified by how much earlier or later the similar motor units were recruited. In order to quantify the recruitment, the difference in the order of recruitment between the pre and post recording will be calculated. Recruitment order of motor units will be

determined through a custom automated search algorithm (Algorithm 1), which will determine the best match between pre- and post-recording motor units.

Algorithm 1: Automated Motor Unit Matching method

Input: Matrix of averaged values from shape and amplitude analysis

Output: Matched pre-post motor units

- 1: **loop** through each pre-motor unit (row) and each post-motor unit (col)
- 2: **if** value at current location is the highest in that row and column, **and** the number is not equal to zero
- 3: **Record** match between the pre- and post- motor unit, and set the row and col to 0 (i.e. remove the pre- and post- motor unit from further pairing)
- 4: Return matched pre-post motor unit pairs

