2.4 Statistical Methods

2.4.1 Surface EMG

An independent samples t-test will be performed on the difference in recruitment position using treatment as the factor for the trapezius muscle. In particular, the statistical test will compare

post-pre capsaicin recruitment differences against post-pre placebo recruitment differences. The average difference in recruitment order will be used to avoid bias of having multiple data points per participant that correspond to different motor units.

2.4.2 *Intramuscular EMG*

From the intramuscular EMG algorithm mentioned in section 2.3.2, the resultant matrices will be the variances for the pre-recording motor unit trains. The statistical model used will assess the difference between the pre- and post- recording motor units for each capsaicin and placebo as well as a between group comparison (Post-Pre capsaicin motor unit variance vs. Post-Pre placebo motor unit variance). These analyses would provide insight into our hypothesis that sensitization induced by capsaicin effects upon the motor unit characteristics. Either an independent samples t-test or a Kruskal-Wallis H test will be performed, depending on how many participants' pre and post motor units match up.

3 Sample Size Calculation

The minimum sample size required per group to detect whether a significant difference exists between two means for one dependent variable was calculated with a confidence level of 95%, a 80% statistical power level and 5% error. A mean detectable difference of 5 for the dependent variable, mean motor unit recruitment change, and an estimated standard deviation of 3 was used. The estimated sample size was 7 people per group; however, considering a 20% drop out rate, the suggested sample size was 9 people per group. This analysis was completed using PASS Software, version 15.

4 Conclusions

This may provide some insights for the neurophysiological influence of central sensitization on changes in efferent responses and movement patterns that occur in patients with persistent pain. However, the clinical implication of this experimental findings on the movement properties needs to be further investigated.

5 References

- [1] IASP, "Classification of chronic pain: descriptions of chronic pain syndromes and definitions of pain terms," *Pain* 1994; Suppl 3: 1–226.
- [2] I. o. Medicine, Relieving Pain in America: A Blueprint for Transforming Prevention, Care, Education, and Research, Washington,DC: The National Academies Press, 2011.

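### Motor units are matched partly on un-normalised amplitude, so a common amplitude change after capsaicin could appear as a recruitment shift or lost matches, and no planned check would show it

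*Combined protocol and SAP*

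**What the plan says.** Section 2.3.1 (Surface EMG) scores every pre/post pair of units on two things. Shape is a normalised cross-correlation, set to zero below 0.8. Amplitude is a ratio of the average amplitudes exported from the decomposition software, where "amplitude ratios that are below a preset threshold of 0.8 or above 1.2 are set to 0". The values not set to zero are averaged into an overall match, and Algorithm 1 pairs the units that score best. The text does not say what happens when only one of the two values is zero, nor which way round the ratio is taken.

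The signed change in recruitment position is averaged over each person's matched units (Section 2.3.1 and Appendix A). Section 2.4.1 compares the arms with an independent t-test. The same section on surface EMG invokes the size principle, under which small units come in before large ones.

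On capsaicin and amplitude, Section 1 says: "A decrease in root mean squared (RMS) amplitude during exercise at the time of peak sensitization was measured by needle EMG". It adds that effects on single units and their recruitment have not been studied.

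Section 3 sizes the trial on this outcome: "A mean detectable difference of 5 for the dependent variable", and "an estimated standard deviation of 3 was used".

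**The concern.** The matching uses a trait that treatment may alter, and under the principle being tested that trait is tied to the outcome. Suppose every unit in a participant's second recording is smaller by the same factor and the order is unchanged. A pre unit's nearest amplitude match is then a post unit that is truly larger and recruited later. Pairing the two gives a positive order difference.

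If all units of one set were paired one to one, the signed differences would average zero. The false shift arises because the largest pre units and the smallest post units go unmatched.

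A fall confined to the capsaicin arm would not be balanced by randomisation. An amplitude effect could then be reported as recruitment reorganisation. Nothing in Sections 2.3 or 2.4 would let a reader tell the two apart.

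**Working it through.** **1. The plan's own figure.** Inputs from Section 3: difference 5, SD 3, 80% power, 5% error (two-sided and 1:1 assumed).
- Normal approximation: 2 × (1.960 + 0.842)² × 3² / 5² = 5.65, so 6 per group.
- Exact noncentral t: power is 0.740 at 6 and 0.816 at 7, so 7 per group, as stated.
- Dropout: 7 / 0.8 = 8.75, so 9, as stated.

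These figures do not depend on the matching rule. The Abstract's twenty participants would give 10 per arm.

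**2. Hand calculation.** Assume 20 units whose amplitudes rise geometrically over a 5-fold span. Neighbours differ by 5^(1/19) = 1.088. If all post amplitudes are multiplied by c, the post unit with the same amplitude as a given pre unit lies −ln(c) × 19 / ln(5) positions later. At c = 0.8 that is 0.223 × 19 / 1.609 = 2.6 positions. The true pair's post/pre ratio is then 0.8, on the edge of the window.

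**3. Simulation with no true reordering.** The documents give none of these inputs, so they are assumed: 20 units, 5-fold span, 3% amplitude noise, true-pair correlation 0.90 to 0.99. Eq. 1 as printed gives negative scores for ratios above one (1 − 1.1 = −0.1), so it is read as 2 − ratio. Mean false shift in positions:

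| Reading of the score | c = 0.9 | c = 0.8 | c = 0.7 |
|---|---|---|---|
| Both values must be non-zero; many false pairs pass the shape filter | +0.5 | +2.3 | +3.9 |
| Same rule; fewer false pairs pass | +0.1 | +1.6 | +3.9 |
| Same rule; no false pair passes | 0.0 | 0.0, with 50% of units matched | no matches |
| Average whatever is non-zero | +0.1 to +1.1 | +0.1 to +2.1 | +0.2 to +2.7 |
| Shape must pass; a zero amplitude is ignored | 0.0 to +0.1 | 0.0 to +0.1 | 0.0 to +0.1 |

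With no amplitude change (c = 1) the shift is about 0.0. For the first row at c = 0.8, varying the inputs over 10 to 30 units and 3- to 10-fold spans gives +0.7 to +5.2.

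A second set of runs (25 units, 80% detected per session, 5% noise, both values required) gives about +0.3, +0.9 and +1.7 at falls of 10%, 15% and 20% when false pairs often pass the shape filter. When few pass, it gives about +0.2, 0 and +0.5.

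**4. Effect on the t-test.** With SD 3, take a false between-arm shift of 1.7:
- 9 per arm: noncentrality 1.7 / (3 × √(2/9)) = 1.20, 16 df, probability of significance 0.20.
- 10 per arm: 1.7 / (3 × √(2/10)) = 1.27, 18 df, probability 0.22.

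At 9 per arm, false shifts of 1, 2 and 3 positions give 0.10, 0.27 and 0.51, against 0.05 nominal.

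**5. The alternatives.** Normalised cross-correlation does not respond to a common scale change, and shape-only matching gave shifts within 0.05 under a common fall. A different scenario was also run: amplitude and order unchanged, but the 5 or 8 largest of 25 units absent after capsaicin. The planned match then stayed near 0. Shape-only matching gave about −0.3 to −2.9, and dividing each recording by its own median gave about −1.1 to −3.2.

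**The case against.** The strongest objection is that the premise is not in the documents. RMS can fall because fewer units fire, or because they fire more slowly, with each unit's amplitude unchanged. Section 1 gives no size for the fall and says single units have not been examined. This stands, and it limits the point to a conditional one. It cuts both ways, however: stable unit amplitude is equally untested, and the matching relies on it.

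Second, amplitude is only part of the score. If shapes are distinctive enough for the 0.8 filter to block every false pair, there is no shift. This also stands, but the cost is then missing matches, concentrated in whichever arm changed.

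Third, no single size can be given until the zero rule and Eq. 1 are settled. That is correct, which is why a range is reported.

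A reader might infer more from two places. In Appendix A all seven differences are positive (mean 58 / 7 = 8.286) and no post unit earlier than position 8 is matched. That fits the artefact, but it is one worked example with no arm stated, and real reordering would look the same. A reader might also take the 55% rejection rate that simulation gives for a shift of 1.68 at 10 per arm. That rate implies an SD of about 1.7; at the plan's SD of 3 it is about 22%.

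**Conclusion.** The concern holds as a vulnerability. Matching uses un-normalised amplitude, nothing corrects a common change, and amplitude is expected to rise with recruitment order. A fall confined to the capsaicin arm could therefore produce a false positive shift, or lose matches in that arm.

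At an assumed 20% fall the false shift runs from about 0 to +2.3 positions in the central settings, and to about +5 in the widest. The range rests on the assumed number and span of units, on how many false pairs pass the shape filter, and on the unstated rule for a zero score.

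The documents do not support saying that capsaicin lowers unit amplitude, that the planned analysis is biased away from the null, or that a positive result would be false. They do show that the plan, as written, could not tell an amplitude change from a change in order.

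**What to change.** Keep the combined score as the primary analysis and add to Sections 2.3.1 and 2.4.1:

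- A pre-specified, descriptive sensitivity analysis that matches on shape alone, with cross-correlation at or above 0.8.
- By arm: the fraction of units matched, the number of units detected before and after, and the median post/pre amplitude ratio of shape-matched pairs.
- A statement that a recruitment shift will be interpreted with caution if the arms differ in amplitude ratio or if the shape-only result disagrees.
- The rule for a pair in which only one of the two values is zero.

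Do not make the shape-only result a veto, and do not substitute median-centred amplitudes. Each creates a false shift of its own if the largest units drop out after capsaicin.

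This is a cheap improvement: some code and wording, data already being collected, and no change to the sample size. The downside is a less accurate sensitivity matcher (about 73 to 76% of pairs correct, against 90% for the combined score with no amplitude change, in the harder simulated case). It is also not neutral if the set of detected units changes, which is why the unit counts should be reported beside it.

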2.3 Study Procedures for EMG Analyses

This section outlines the procedures for the EMG analysis. For the sEMG data, the pre-recording motor units will be matched with an algorithm implemented in MATLAB (Mathworks, version 2018a), described in section 2.3.1, in order to determine the aberration of recruitment pattern after treatment.

For the iEMG data, the pre- and post-recording motor units will also be matched using an algorithm implemented in MATLAB (Mathworks, version 2018a), described in 2.3.2. The variability of that motor unit shape will be compared before and after capsaicin and between groups.

2.3.1 *Surface EMG*

Recorded sEMGs will be analyzed in *Neuromap* [32], which provides an average template, average amplitude, and order of recruitment of each motor unit detected and isolated from the raw signal using *Delsys*' motor unit decomposition algorithm [33]. Each motor unit template will then be analyzed based on their “overall match” in shape and amplitude.

Shape Analysis

The motor unit signal that will be obtained from M electrode contacts at T consecutive time samples will be assembled into an $M \times T$ matrix. This matrix will then be compressed into a single vector to create a motor unit “signature” [34]. This will be done by taking the recordings from all electrode contacts at a single time step and concatenating it to the recordings from all contacts at the next time point. This concatenation will be repeated to the time T to create the signature (**Figure 1**). This process will be performed for the pre- and post-recording motor units for each participant.

The shape of each detected pre-recording motor unit will be compared to the shape of each post-recording motor unit via the cross-correlation function, *xcorr*, in *Matlab* (Mathworks, 2018a). This function returns a normalized value between 0 – 1 between each pre- and post-recording motor unit. Cross-correlation values between pre- and post-recording motor unit pairs that are

below a preset threshold of 0.8 [35] will be set to 0 as the pair is unlikely to be from the same motor unit.

Amplitude Analysis

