The average recruitment order difference for each motor unit will be obtained for each participant. Following this, for each participant, the recruitment difference for all of their motor units will be averaged, to obtain one vector of average recruitment changes per person. This final matrix containing numbers on a continuous scale, will be used for statistical testing. See Appendix A for a detailed explanation of the matrix set up.

2.3.2 *Intramuscular EMG analysis using template matching*

Recorded iEMGs will be thresholded using the median absolute deviation estimate approach (**Eq.2**) to find the peak location of motor unit action potentials (MUAPs) [36].

$$Threshold = 10 \times \frac{Median(|X|)}{0.6745} \quad (2)$$

Each detected peak, along with 12.5 ms before and after will be stored and used for analyses. These detected MUAPs will then be clustered to determine the number of motor units present in the recording. In particular, the first detected peak and its surrounding environment (i.e. the MUAP) forms the first motor unit template. Subsequent detected MUAPs will be compared to the first template using cross correlation. If the cross correlation is more than 0.85, it will be determined as the same MUAP and added to that motor unit cluster and the template will be updated. However, if the cross-correlation is less than 0.85, it will be classified as a different motor unit and a new template cluster will be created for comparison.

This process will be repeated until all of the detected MUAPs in the pre- and post-recording are classified. The MUAP cluster with the highest number of MUAPs, for the pre-recording, will be compared with all MUAP clusters found in the post-recording for each participant. The MUAP cluster in the post that has the highest cross-correlation value will be considered “matched.” Participants that do not have matched MUAPs with cross-correlation values above or equal to 0.95 will not be used for statistical analysis.

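### The surface EMG matching rule never says that a motor-unit pair must pass both the shape and the amplitude threshold, so as written a pair that fails one can still be matched

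*Combined protocol and SAP*

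**What the plan says.** Section 2.3.1 builds an overall match for every pre/post pair of motor units, described as a match "in shape and amplitude".

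- **Shape Analysis:** cross-correlations "below a preset threshold of 0.8 [35] will be set to 0 as the pair is unlikely to be from the same motor unit".
- **Under Amplitude Analysis:** "Similar to the shape analysis, amplitude ratios that are below a preset threshold of 0.8 or above 1.2 are set to 0". Ratios above 1 are then rescaled by Eq. 1.
- **Combination:** "The numbers from the shape analysis and amplitude analysis, which are not set to 0, will be averaged together" to give the overall match.
- **Algorithm 1:** its input is the "Matrix of averaged values from shape and amplitude analysis". It records a pair when the cell is the highest in its row and column and "the number is not equal to zero", then removes both units from further pairing.
- **Use of the matches:** for each participant, "the recruitment difference for all of their motor units will be averaged". Section 2.4.1 compares "post-pre capsaicin recruitment differences against post-pre placebo recruitment differences" by an independent samples t-test.

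**The concern.** The two thresholds exist to keep different motor units from being paired. They do so only if failing either one removes the pair. The combination sentence attaches its exclusion to the numbers, not to the pairs. Followed as written, a zeroed score drops out of the average and the other score stands alone. Algorithm 1 cannot repair this: it receives only the combined value, has no minimum score other than being non-zero, and cannot see which threshold failed. A pair that the plan itself considers unlikely to be one unit could then be the best match in its row and column.

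At stake is the surface EMG endpoint. The per-person mean recruitment change rests on these matches, and it is also the variable on which section 3 sizes the study (difference 5, SD 3). By contrast, section 2.3.2 does state a final acceptance rule for the intramuscular recordings: a matched correlation of at least 0.95.

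**Working it through.** **1. Score ranges from the plan's own thresholds** (shape at least 0.8; ratio 0.8 to 1.0, so Eq. 1 is not used)

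- Both pass: (0.8 + 0.8)/2 = 0.80 to (1 + 1)/2 = 1.00.
- One fails, average of the numbers not set to 0: the surviving score alone, 0.80 to 1.00.
- One fails, zeros counted: (0.8 + 0)/2 = 0.40 to (1 + 0)/2 = 0.50.

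Under the literal reading the score cannot separate a pair passing both thresholds from a pair failing one. With zeros counted, a failing pair cannot outrank a passing pair of this kind, but it is non-zero and can be recorded as a leftover match.

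**2. A small case through Algorithm 1** (assumed values, chosen to show what is possible)

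Pre units are A and B; post units are A' and X. The only true pair is A–A'. Ratios are taken as post/pre and are mutually consistent: 2.0 × 0.90/0.99 = 1.82.

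| Pair | Shape | Ratio | Literal | Zeros counted | Both required |
|---|---|---|---|---|---|
| A–A' | 0.92 | 0.90 | 0.91 | 0.91 | 0.91 |
| A–X | 0.30 (set to 0) | 0.99 | 0.99 | 0.495 | 0 |
| B–A' | 0.30 (set to 0) | 1.82 (set to 0) | 0 | 0 | 0 |
| B–X | 0.93 | 2.0 (set to 0) | 0.93 | 0.465 | 0 |

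- Literal: A–X is recorded and removes A and X; B–A' is 0. One match, none correct.
- Zeros counted: A–A' is recorded, then B–X. Two matches, one correct.
- Both required: A–A' only. One match, correct.

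**3. What a false pair does to the endpoint**

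Appendix A's figure first: the post positions sum to 98 and the pre positions to 40, so (98 − 40)/7 = 58/7 = 8.286, as printed. Any re-pairing among these same 7 pre and 7 post units leaves the two sums, and so 8.286, unchanged. The mean can move only when a false pair adds a unit or displaces one.

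*Displacement.* If pre unit 1 (matched to post 9) is instead matched to an unlisted post position, the mean changes by (new − 9)/7. With post 3 it is (58 − 6)/7 = 7.43; with post 17 it is (58 + 8)/7 = 9.43.

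*Added pairs.* Assume that the 7 listed pairs are correct, that 14 pre units were detected, and that k extra pairs form by chance among the unlisted units. The unlisted pre positions (3, 7, 9 to 13) have mean 65/7 = 9.286. With N post units detected, the unlisted post mean is (N(N + 1)/2 − 98)/(N − 7). The expected mean is (58 + k × d)/(7 + k), where d is the unlisted post mean minus 9.286.

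| Post units assumed | d | k = 1 | k = 3 | k = 7 |
|---|---|---|---|---|
| 19 | −1.619 | 7.05 | 5.31 | 3.33 |
| 25 | 3.325 | 7.67 | 6.80 | 5.81 |
| 32 | 7.914 | 8.24 | 8.17 | 8.10 |
| 33 | 8.522 | 8.32 | 8.36 | 8.40 |
| 40 | 12.593 | 8.82 | 9.58 | 10.44 |

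The expected mean falls below 8.29 with up to 32 post units and rises above it from 33. Appendix A does not give the number of units detected.

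**The case against.** The strongest reply is that both thresholds were plainly intended. The sentence speaks of averaging two numbers together, and a lone survivor has nothing to be averaged with. The overall match is described as one of shape and amplitude jointly. The reason given for zeroing a poor shape score is a statement about the pair, and the amplitude rule is introduced as working in the same way. On this view the clause means that only pairs with neither number zeroed are averaged, and the fault is loose drafting. If the code does that, no result changes.

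This stands as a plausible account of intent. It does not supply the missing rule: no sentence sets the overall match to 0 when one score fails, Algorithm 1 does not enforce it, and the three readings give three different match sets in the case above.

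Two further objections also stand. The small case is constructed, so it shows possibility and not frequency. And the same rule applies to both arms.

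A reader might infer that false matches dilute a true shift. The Appendix A illustration gives that impression if only 19 post units are assumed, the smallest total consistent with the listed positions, but the sign reverses at larger totals. The documents therefore do not support a claim of attenuation. Nor do they support a claim of a specific loss of power, of added noise, of a false group difference, or that the code actually behaves this way.

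**Conclusion.** The concern holds as a defect in the stated rule. Followed literally, the text lets a pair failing one threshold score 0.80 to 1.00 and be matched or displace a true pair; counting the zeros lowers the score to 0.40 to 0.50 but still allows a match. These ranges follow from the plan's thresholds alone, for ratios of 0.8 to 1.0.

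The consequence is conditional. If the code follows the text, differences between different motor units can enter the per-person mean. The frequency, size and direction of the effect cannot be derived from the documents; the Appendix A figures are a sensitivity illustration on assumed unit counts, from a single worked example that is itself output of the matching. The sample size of 7, then 9, per group is unaffected, because it does not use the matching rule. The point should be fixed, with medium confidence that it affects the data.

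**What to change.** - Correct Eq. 1 first. As printed it gives 0 to −0.2 for ratios from 1 to 1.2, so a pair with shape 0.90 and ratio 1.10 would score (0.90 − 0.10)/2 = 0.40 despite passing both thresholds. Any stated form that maps ratios above 1 and up to 1.2 into the 0 to 1 scale would serve.
- Then state that the overall match equals (shape + normalized amplitude)/2 only if both scores pass their thresholds, and is 0 otherwise.
- Check that the MATLAB code does this, and rerun the matching if it does not. Appendix A already reports assumption-check p-values, so the matching may have been run.
- Report the number of matched units per participant and arm.

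The cost is one sentence for the rule, the Eq. 1 correction and, if the code follows the text, about one line of code and a rerun on the existing recordings. The downside is fewer matched units per person, so each mean rests on fewer units. A participant with no pair passing both thresholds would have no value for the t-test, and the plan should say how that is handled.
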